3.3.2 Secondary Efficacy Endpoints

Duration of anti-SARS-CoV-2 S antibody titers and antibody neutralization in the year following the additional dose of vaccine
SARS-CoV-2 PCR positivity
Symptomatic COVID-19
COVID-19 requiring hospitalization
Longitudinal changes in log SARS-CoV-2 antibody titer during the study

3.3.3 Exploratory Endpoints

Anti-S1 and anti-RBD serology
Detection of SARS-CoV-2 spike protein in blood after the additional dose of vaccine
Additional serological panels and correlates of neutralizing antibody
SARS-CoV-2 virology, diagnostics, and sequencing, including novel variants of concern
Oral fluid anti-N and anti-S immunoglobulin levels (IgA, IgM, IgG)
Antigen-specific B cell response
Antigen-specific T cell response
Evidence of immune activation, transcriptomics and cytokine signaling
Durability of de novo donor-specific anti-HLA antibody

3.4 Stratification, Randomization, and Blinding/Masking

This is an open-label study.

4. Selection of Participants and Clinical Sites/Laboratories

4.1 Rationale for Study Population

This study will enroll individuals who have completed primary series of mRNA COVID-19 vaccine and have a negative or low (≤ 2500 U/mL) antibody response measured at least 30 days after the last dose of vaccine. This group of patients is at high risk for severe COVID-19 disease due to pharmacologic immunosuppression and a high prevalence of non-transplant risk factors such as obesity and diabetes.

4.2 Inclusion Criteria

Individuals who meet all the following criteria are eligible for enrollment as study participants:

1. Able to understand and provide informed consent.
2. Individual ≥ 18 years of age.
3. Recipient of a kidney or liver transplant ≥ 12 months prior to enrollment, without allograft rejection in the 6 months preceding enrollment.
4. Negative for anti-donor HLA antibodies at screening (central lab).
5. Currently taking one of the following CNJ-based immunosuppressive regimens:
 - Tacrolimus plus MMF or MPA, with or without a corticosteroid
 - Tacrolimus with trough ≥ 5 ng/mL with or without ≤ 5 mg of prednisone or equivalent
6. Received a minimum of 3 doses of either the Moderna COVID-19 Vaccine or Pfizer-BioNTech COVID-19 Vaccine.
7. Participant must be ≥ 60 days after completion of primary vaccination or receipt of the most recent booster dose with any authorized or approved monovalent or bivalent COVID-19 vaccine at the time of study vaccine.
8. Serum antibody negative or low (titer ≤ 2500 U/mL) at ≥ 30 days from the last dose of mRNA COVID-19 vaccine and ≥ 30 days following receipt of a monoclonal antibody product or convalescent plasma for COVID-19, measured using the Roche Elecsys® anti-SARS-CoV-2 S assay.
9. Participant's transplant physician or midlevel practitioner who is clinically licensed to prescribe and manage immunosuppression must confirm the participant's eligibility based on medical history.

4.3 Exclusion Criteria

Individuals who meet any of these criteria are not eligible for enrollment as study participants:

1. Currently on an IS regimen different from the two regimens described in the Inclusion Criteria, for example (but not limited to) those including sirolimus, everolimus, belatacept, or azathioprine.
2. Recipient of any allograft other than a kidney or liver.
3. Participant is pregnant.
4. Any past history of Donor Specific Antibody (DSA) using local site standards.
5. Currently taking any systemic immunosuppressive agent, other than their prescribed transplant immunosuppression.
6. Known history of severe allergic reaction to any component of an authorized or licensed COVID-19 vaccine.
7. Thrombotic events, myocarditis, or pericarditis temporally associated with a prior dose of COVID-19 vaccine.
8. History of heparin-induced thrombocytopenia.

9. Any change in transplant immunosuppression regimen (drug or dose) in response to suspected or proven rejection within the last 6 months.
10. Significant graft dysfunction (*see study definitions*).
11. Receipt of any cellular depleting agent (e.g. ATG, rituximab, alemtuzumab, Cyclophosphamide) within 12 months preceding enrollment.
12. Concurrent autoimmune disease at risk for exacerbation with immunosuppression reduction.
13. Any untreated active infection including BK viremia $>10^4$ copies.
14. Infection with HIV.
15. Recent (within one year) or ongoing treatment for malignancy with the exception of (1) non-melanomatous skin cancer definitively treated by local therapy, and (2) definitively treated carcinoma-in-situ of the cervix (Stage 0 cervical cancer)
16. Receipt of a monoclonal antibody product or convalescent plasma within the last 30 days.
17. Any past or current medical problems, treatments, or findings which, in the opinion of the investigator, may pose additional risks from participation in the study, may interfere with the candidate's ability to comply with study requirements or may impact the quality or interpretation of the data obtained from the study.

4.4 Selection of Clinical Sites

This study will be conducted at approximately 15 clinical sites across the United States that have transplant programs with the population described in the protocol and which are able to comply with the requirements of the protocol. Sites may be added or withdrawn to meet the accrual goals outlined in the protocol.

5. Known and Potential Risks and Benefits to Participants

The risks cited below reflect the information currently included in the Moderna and Pfizer-BioNTech Package Inserts and Emergency Use Authorizations. The safety data accrued with the bivalent vaccines (Original and Omicron BA.1) and with the original COVID-19 vaccines are relevant to the updated 2023-2024 formulations because these vaccines are manufactured using the same process.

5.1 Risks of the Investigational Products as cited in the Full FDA EUA Prescribing Information

5.1.1 Risks of Moderna COVID-19 Vaccine (includes original, bivalent, and 2023-2024 formula)

The most common side effects reported include injection site reactions (pain, redness and swelling), axillary swelling/tenderness, fatigue, headache, myalgia, arthralgia, chills, and nausea/vomiting. Severe allergic reactions, including anaphylaxis, have been reported following the administration during mass vaccination outside of clinical trials. Severe allergic reactions included difficulty breathing, swelling of the face and throat, rash, dizziness, and weakness. Other risks include increased risks of myocarditis (inflammation of the heart muscle) and pericarditis (inflammation of the tissue surrounding the heart) following vaccination.

Additional adverse reactions, some of which may be serious, may become apparent with post-authorization use of the vaccine.

5.1.2 Risks of Pfizer-BioNTech COVID-19 Vaccine (includes original, bivalent, and 2023-2024 formula)

The most common side effects reported include non-severe allergic reactions (rash, itching, hives and facial swelling), injection site reactions (pain, redness and swelling), fatigue, headache, myalgia, arthralgia, chills, fever, lymphadenopathy, vomiting, diarrhea, arm pain and general malaise. Severe allergic reactions that include difficulty breathing, swelling of the face and throat, rash and dizziness or weakness have been reported post authorization but are less common. Other risks include increased risks of myocarditis (inflammation of the heart muscle) and pericarditis (inflammation of the tissue surrounding the heart) following vaccination.

Additional adverse reactions, some of which may be serious, may become apparent with post-authorization use of the vaccine.

5.2 Risks of Moderna COVID-19 Vaccine and Pfizer-BioNTech Vaccine in adults as cited in Medical Literature (includes original, bivalent, and 2023-2024 formulas)

The Moderna COVID-19 Vaccine and Pfizer-BioNTech COVID-19 Vaccine are being administered under an Emergency Use Authorization. Adverse Events that occur outside of clinical trials as a result of the mass vaccination effort are reported to each manufacturer and included in a Fact Sheet for Healthcare Providers.^{33,34}

In a recent cohort of 741 organ transplant recipients who received two doses of either the Moderna or Pfizer-BioNTech vaccine, reactogenicity was similar to what has been reported in immunocompetent people: pain at injection site, fatigue, and headache were common. Severe reactogenicity (defined as preventing daily activity) occurred in 1-2% of study participants. Systemic reactogenicity was more common after the second dose of vaccine. There was an increased risk of local reactogenicity among recipients who

were maintained on an immunosuppressive regimen that included corticosteroids or mTOR inhibitors, and also among those who received the Moderna vaccine. There were no cases of anaphylaxis. There was one case of acute allograft rejection after the second dose of vaccine.³⁶

Infrequent cases of myocarditis or pericarditis have been reported after the use of COVID-19 vaccines containing the SARS-CoV-2 S-antigen. Myocarditis and pericarditis have been reported in greatest numbers in males under the age of 40 years following a second dose of mRNA vaccines, but cases have been reported in older males and in females as well, and also following other doses, and other vaccine platforms, including after doses of an adjuvanted protein vaccine. The observed risk is highest in males 12 to 17 years of age. While some cases required intensive care support, available data from short-term follow-up suggest that symptoms resolve in most individuals with conservative management. Information is not yet available about potential long-term sequelae. The risk in children younger than 12 years old is currently being assessed, and both the size of the database and length of follow-up in this population are relatively smaller than that of those older than 12 years old. Therefore, the characterization of the risk in children younger than 12 years old is not as well-known as in adolescents and adults.

5.3 Risks Associated with IS Reduction

Any decrease in dose or frequency of immunosuppressive medications in a transplant recipient carries the risk of alloimmune activation leading to acute cellular rejection, subclinical rejection, acute or chronic antibody-mediated rejection, and/or the formation of de novo DSA. The inclusion criteria and the specific immunomodulatory strategies have been designed to minimize, but do not eliminate, this risk. Study participants undergoing IS reduction will be closely monitored for evidence of graft injury and will be returned to their baseline immunosuppressive regimen should graft injury be evident. In addition, subjects will be monitored for the development of de novo DSA throughout the study period.

5.4 Potential Risks to Study Population

There may be an increased risk of low-to-moderate reactogenicity to trial participants who receive an additional dose of vaccine. Based on currently available information, the risk of serious allergic events is likely to be extremely low, equal to or less than has been seen in the immunocompetent population. There is no evidence that the COVID-19 vaccine will result in new alloimmune events, and none are expected.

5.5 Risks of Other Protocol Specified Medications

Not Applicable

5.6 Risks of Study Procedures

5.6.1 Risk of Blood Draw

Collection of blood may cause slight discomfort, pain, bleeding or bruising at the injection site. Rarely, fainting or infection may occur.

5.6.2 Risks Associated with Nasal Mid-Turbinate Swab Collection

Nasal mid-turbinate swab collection may cause localized discomfort. Rarely, mild epistaxis may occur.

5.6.3 Risks Associated with Oral Fluid Collection

Oral fluid collection may result in mild irritation where the gums are swabbed.

5.6.4 Risk of Internet Based Data Collection

Data from this study will be entered into a computerized database through a secured web site. All information will be saved and transmitted in a coded form. Only authorized personnel requiring a password will be permitted to enter data. There is risk, although minimal, of unauthorized persons obtaining confidential information.

5.7 Potential Benefits

There might be no benefit to participants in this study. If a participant achieves an increased level of antibody against SARS-CoV-2 as a result of participating in this study, there might be associated benefit. However, whether any participant will achieve this is unknown.

6. Investigational Agents

The study products used in this protocol are the: Moderna COVID-19 Vaccine and the Pfizer-BioNTech COVID-19 Vaccine. The doses provided for the study will be according to the current CDC and FDA Emergency Use Authorizations. The current available CDC recommended vaccines are provided to the clinical sites.

6.1 Investigational Agent #1: Moderna COVID-19 Monovalent Vaccine (Protocol v1.0-5.0)

The Moderna COVID-19 monovalent vaccine will no longer be offered for the study.

6.2 Investigational Agent #2: Pfizer-BioNTech COVID-19 Monovalent Vaccine (Protocol v1.0-5.0)

The Pfizer-BioNTech COVID-19 monovalent vaccine will no longer be offered for the study.

6.3 Investigational Product #3: Moderna Bivalent COVID-19 Vaccine (Protocol v6.0-7.0)

The Moderna Bivalent COVID-19 Vaccine (Original and Omicron BA.4/BA.5), hereafter referred to as Moderna Bivalent COVID-19 Vaccine will no longer be offered for this study

Commented [MOU1]: I can either add sections addressing the adapted monovalent vaccines or we modify this section to be generic and refer to the most current vaccine?

6.4 Investigational Product #4: Pfizer-BioNTech Bivalent COVID-19 Vaccine (Protocol v6.0-7.0)

Pfizer-BioNTech Bivalent COVID-19 Vaccine (Original and Omicron BA.4/BA.5, hereafter referred to as Pfizer-BioNTech Bivalent COVID-19 Vaccine will no longer be offered for this study.

6.5 Investigational Product #5: Moderna COVID-19 Vaccine, Spikevax® 2023-2024 Formula (Protocol v8.0 and beyond)

The updated Moderna COVID-19 Vaccine, Spikevax® 2023-2024 Formula, hereafter referred to as Moderna COVID-19 Vaccine 2023-2024 is being used in the study to provide an FDA approved dose of vaccine to eligible participants.

6.5.1 Formulation, Packaging, and Labelling

Moderna COVID-19 Vaccine 2023-2024 is supplied as a frozen suspension in multiple-dose vials, single dose vials, and single dose pre-filled syringes that do not contain a preservative and must be thawed prior to administration. Clinical sites will be provided with the formulation available to the study.

Each 0.5 mL dose of the Moderna COVID 19 Vaccine 2023-2024 contains 50 mcg of nucleoside-modified messenger RNA (mRNA) encoding the pre-fusion stabilized S-glycoprotein of SARS-CoV-2 Omicron variant lineage XBB.1.5.

Each 0.5 mL dose also contains the following ingredients: a total lipid content of 1.01 mg (SM-102, polyethylene glycol [PEG] 2000 dimyristoyl glycerol [DMG], cholesterol, and 1,2-distearoyl-sn-glycero-3-phosphocholine [DSPC]), 0.25 mg tromethamine, 1.2 mg tromethamine hydrochloride, 0.021 mg acetic acid, 0.10 mg sodium acetate trihydrate, and 43.5 mg sucrose.

6.5.2 Dosage, Preparation, and Administration

The Moderna COVID-19 Vaccine 2023-2024 dose used in the study will be a single dose of 50 mcg (0.5 mL) administered in the deltoid muscle.

Vaccine preparation and administration details will follow the package insert and be recorded on the appropriate eCRF.

6.6 Investigational Product #4: Pfizer-BioNTech COVID-19 Vaccine, Comirnaty® 2023-2024 Formula (Protocol v8.0 and beyond)

The updated Pfizer-BioNTech COVID-19 Vaccine, Comirnaty® 2023-2024 Formula, hereafter referred to as Pfizer-BioNTech COVID-19 Vaccine 2023-2024 is being used in the study to provide an FDA approved dose to eligible participants.

6.6.1 Formulation, Packaging, and Labelling

Pfizer-BioNTech COVID-19 Vaccine 2023-2024 is supplied in single dose vials and single dose prefilled syringes. It is supplied as a frozen suspension that does not contain preservative. Clinical sites will be provided with the formulation available to the study.

Each 0.3 mL dose of Pfizer-BioNTech COVID-19 Vaccine 2023-2024 is formulated to contain 30 mcg of a nucleoside modified messenger RNA (modRNA) encoding the viral spike (S) glycoprotein of SARS-CoV-2 Omicron variant lineage XBB.1.5 (Omicron XBB.1.5).

Each 0.3 mL dose of Pfizer-BioNTech COVID-19 Vaccine 2023-2024 also includes the following ingredients: lipids (0.43 mg ((4- hydroxybutyl)azanediyl)bis(hexane-6,1-diyl)bis(2-hexyldecanoate), 0.05 mg 2-(polyethylene glycol 2000)-N,N-ditetradecylacetamide, 0.09 mg 1,2-distearoyl-sn-glycero-3-phosphocholine, and 0.19 mg cholesterol), 0.06 mg tromethamine, 0.4 mg tromethamine hydrochloride, and 31 mg sucrose.

6.6.2 Dosage, Preparation, and Administration

The Pfizer-BioNTech COVID-19 Vaccine 2023-2024 dose used in this study will be a single dose of 30 mcg (0.3 mL) administered intramuscularly in the deltoid muscle.

Vaccine preparation and administration details will follow the package insert and be recorded on the appropriate eCRF.

6.7 Immunosuppression Reduction

6.7.1 Immunosuppression (IS) Reduction

Participants on a tacrolimus-based regimen that includes MMF (or equivalent), with or without corticosteroid:

MMF (or equivalent) will be withheld for five days prior to and 2 weeks following vaccine administration. During the interval that MMF is withheld, no adjustments will be made to the CNI or corticosteroid dose.

Participants on a tacrolimus based regimen with a trough level ≥ 5 ng/mL, with or without ≤ 5 mg Prednisone (or equivalent) and no MMF or other antimetabolite

Reduce CNI by 25% of starting dose for 5 days prior to and 2 weeks following vaccine administration.

6.8 Drug Accountability

Under Title 21 of the Code of Federal Regulations (21CFR §312.62) the investigator will maintain adequate records of the disposition of the investigational agent, including the date and quantity of the drug received, to whom the drug was dispensed (participant-by-participant accounting), and a detailed accounting of any drug accidentally or deliberately destroyed.

Records for receipt, storage, use, and disposition will be maintained by the study site. A drug-dispensing log will be kept current for each participant. This log will contain the identification of each participant and the date and quantity of drug dispensed.

All records regarding the disposition of the investigational product will be available for inspection.

6.9 Assessment of Participant Compliance with Investigational Agent

Not applicable due to the fact that the assigned COVID-19 vaccine will be a single dose administered by qualified personnel at the study site.

6.10 Toxicity Prevention and Management

The vaccine will be administered by qualified personnel in dedicated observation rooms. Participants will be monitored for allergic reactions or other intolerance for 30 minutes following vaccine administration. Appropriate medications to address allergic reactions will be supplied by the investigational pharmacy (i.e., epinephrine, anti-histaminergic medications) and there is access to local rapid response team support in case of serious adverse events.

6.11 Premature Discontinuation of Investigational Agent

Not applicable due to the fact that the additional dose of COVID-19 vaccine that will be administered under this protocol is a single dose.

6.12 Premature Discontinuation of IS Reduction

Monitoring for evidence of rejection during IS reduction is described in Section 8.3.3. A persistent increase in creatinine (for kidney recipients) or of ALT (for liver recipients) will be cause for return to baseline IS, as follows:

For kidney transplant recipients: A finding of a 0.3mg/dL or 25% elevation (whichever is higher) of serum creatinine over baseline (pre-reduction in IS) will be repeated in 1-3 days. If the elevation persists or increases, the subject will return to his/her baseline immunosuppression regimen. Further management will be determined by the treating transplant physician. If the serum creatinine returns to baseline without further treatment, the event will not be recorded as rejection. If the participant requires more than baseline levels of IS or receives specific treatment for rejection, the event will be recorded as rejection.

For liver transplant recipients: A finding of an elevation of an ALT >2X baseline (pre-reduction in IS) or >60 IU/L if the baseline ALT is <30 IU/L will be repeated in 1-3 days. If the elevation persists or increases, the subject will return to his/her baseline immunosuppression regimen. Further management will be determined by the treating transplant physician. If the ALT returns to baseline without further treatment,

the event will not be recorded as rejection. If the participant requires more than baseline levels of IS or receives specific treatment for rejection, the event will be recorded as rejection.

7. Other Medications

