13.4.4	Analyses of Exploratory Objectives	53
13.4.5	Descriptive Analyses	53
13.5	Interim Analyses	53
13.5.1	Interim Analysis of Efficacy Data	53
13.5.2	Interim Analysis of Safety Data	53
13.6	Statistical Hypotheses	53
13.7	Sample Size Considerations	53
14.	Identification and Access to Source Data	55
14.1	Source Data	55
14.2	Access to Source Data	55
15.	Quality Assurance and Quality Control	56
16.	Protocol Deviations	57
16.1	Protocol Deviation Definitions	57
16.2	Reporting and Managing Protocol Deviations	57
17.	Ethical Considerations and Compliance with Good Clinical Practice	58
17.1	Statement of Compliance	58
17.2	Informed Consent Process	58
17.3	Privacy and Confidentiality	58
18.	Publication Policy	59
19.	References	60

Appendix 1: Screening (All Participants)	65
Appendix 2: Schedule of Events (COVID-19 Vaccine Dose Alone).....	66
Appendix 3: Schedule of Events (IS Reduction plus COVID-19 Vaccine Dose).....	67

Glossary of Abbreviations

ATG	Anti-thymocyte globulin
CFR	Code of Federal Regulations
CRF	Case Report Form
CTCAE	Common Terminology Criteria for Adverse Events
DAIT	Division of Allergy, Immunology, and Transplantation
dnDSA	De novo Donor Specific Antibody
DSA	Donor Specific Antibody
EUA	Emergency Use Authorization
DSMB	Data Safety Monitoring Board
FDA	Food and Drug Administration
GCP	Good Clinical Practice
ICH	International Conference on Harmonization
IND	Investigational New Drug
IRB	Institutional Review Board
IS	Immunosuppression
MOP	Manual of Procedures
NIAID	National Institute of Allergy and Infectious Diseases
PI	Principal Investigator
PrEP	Pre-Exposure Prophylaxis
SAE	Serious Adverse Event
SAP	Statistical Analysis Plan
SAR	Suspected Adverse Reaction
SOP	Standard Operating Procedure
SOT	Solid Organ Transplant
SUSAR	Serious Unexpected Suspected Adverse Reaction
ULN	Upper Limit of Normal

Study Definitions Page

Acute Rejection	
Acute Cell-Mediated Rejection, Biopsy Proven: Rejection (including borderline) graded according to 2019 Banff Criteria.
 
Antibody-Mediated Rejection: A clinical and histologic event that meets the Banff 2019 criteria for antibody mediated rejection.
 
Clinically Diagnosed and Treated Rejection: Any clinical event, with or without supporting evidence from a biopsy, which the treating physician diagnoses as “rejection” AND for which the patient is treated with steroids, lytic therapy, or an increase in dose or number of immunosuppressive medications.

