Acute Myocarditis / Acute Pericarditis	Myocarditis is inflammation of the heart muscle. Pericarditis is inflammation of the lining outside the heart. In this study, the definition of suspected or confirmed acute myocarditis or acute pericarditis is the Centers for Disease Control and Prevention (CDC) case definition criteria: https://www.cdc.gov/mmwr/volumes/70/wr/mm7027e2.htm
Basic Metabolic Panel	Includes sodium, potassium, chloride, carbon dioxide (CO ₂) total, blood urea nitrogen, creatinine, glucose, calcium, anion gap and BUN/creatinine ratio.
Comprehensive Metabolic Panel	Includes sodium, potassium, chloride, carbon dioxide (CO ₂) total, blood urea nitrogen, creatinine, glucose, calcium, total protein, albumin, total bilirubin, alkaline phosphatase (Alk Phos), aspartate aminotransferase (AST), alanine aminotransferase (ALT), anion gap, BUN/creatinine ratio, and AST/ALT ratio.
Donor Specific Antibodies (DSA)	Antibodies directed at donor human leukocyte antigens (HLA) by central lab assessment.
Graft Failure	
Kidney: Any of the following events: renal dialysis of more than 3 months duration; listing for re-transplantation; death from kidney failure.
 
Liver: Re-listing for transplantation or death from liver failure.

IS Reduction Failure	Participant resumes baseline IS per the criteria outlined in Section 6.7 Premature Discontinuation of IS Reduction but does not receive definitive treatment for rejection e.g. thymoglobulin, steroids, or a sustained increase in dose or number of immunosuppressive medications.
Lost to Follow-up	Missing primary endpoint assessment and/or final study visit.
Medical Monitor	The physician who is responsible for Sponsor oversight of safety aspects of the trial. The medical monitor will determine the attribution of Serious Adverse Events after considering all investigator input.
Significant Graft Dysfunction for Study Eligibility	
Kidney: eGFR <35mL/min/1.73m².
 
Liver: INR >ULN (in patients not on anticoagulation), direct bilirubin >1.

Negative or indeterminate Antibody Titer	A measurement of <0.8 U/mL using the Roche Elecsys® anti-SARS-CoV-2 S assay.

NIAID Project Manager	NIAID assigned project manager who is responsible for all day to day administrative protocol-related issues, including version control, consent review, etc.

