2.1 Hypotheses

Kidney and liver transplant recipients who had a negative or low (≤ 2500 U/mL) anti-SARS-CoV-2 S response (using the Roche Elecsys® assay) to a completed primary series of the Moderna COVID-19 Vaccine or the Pfizer-BioNTech COVID-19 Vaccine will develop an enhanced SARS-CoV-2 antibody response after receiving a dose of study vaccine, with or without reduction of their maintenance transplant immunosuppression regimen.

Temporary reduction of maintenance immunosuppression as directed in this protocol will result in higher fold increase in antibody titer than achieved in those who do not have IS reduction, without an increased risk of alloimmune events (rejection or development of dnDSA).

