11.5 Study Pausing Rules

If the following occur, relevant study interventions will be temporarily halted pending a DSMB review and recommendation as to whether the study may proceed.

1. Any Grade 4 or 5 event that is definitely or possibly attributed to the study dose of vaccine or to immunosuppression reduction.
2. Any probable or confirmed case of either acute myocarditis or acute pericarditis that occurs within 6 weeks of the study vaccine.
3. **Excess incidence of acute rejection (clinically treated or biopsy-proven):** Based on registry data, approximately 5-6 rejection events would be expected over the course of the study, independent of any effect of the study interventions. A pausing rule has been constructed such that the study would be paused if there is a >50% chance that the observed event rate exceeds three times the expected rate. The pausing rule will be applied to the study by group: (1) COVID-19 vaccine dose alone (2) MMF withdrawal (3) CNI reduction. Event rates triggering a pause are shown below:

Number of participants	Number of events required to trigger a pause	Event rate required to trigger a pause
10	3	30%
20	3	15%
30	3	10%
40	4	10%
50	4	8%
75	4	5%
100	5	5%
150	6	4.0%

200	7	3.5%
250	8	3.2%
300	9	3.0%
350	10	2.9%
400	11	2.8%

4. **Excess incidence of graft loss:** Based on registry data, it is expected that there will be approximately 6-7 graft losses over the course of the study, independent of any effect of the study interventions. A pausing rule has been constructed such that the study would be paused if there is a >50% chance that the observed event rate exceeds three times the expected rate. The pausing rule will be applied to the study by group: (1) COVID-19 vaccine dose alone (2) MMF withdrawal (3) CNI reduction. Event rates triggering a pause are shown below:

Number of participants	Number of events required to trigger a pause	Event rate required to trigger a pause
10	3	30%
20	3	15%
30	3	10%
40	4	10%
50	4	8%
75	4	5%
100	5	5%
150	6	4.0%
200	7	3.5%
250	8	3.2%
300	9	3.0%
350	10	2.9%
400	11	2.8%

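### Section 6.12 can drop rejection episodes from the count in the reduction arm only, in conflict with the Acute Rejection definition and the rejection pausing rule

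*Combined protocol and SAP*

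**What the plan says.** Section 6.12 applies to participants on IS reduction. A creatinine rise (kidney) or ALT rise (liver) above a threshold is repeated in 1-3 days. If it persists, "the subject will return to his/her baseline immunosuppression regimen". The recording rule for kidney recipients follows: "If the serum creatinine returns to baseline without further treatment, the event will not be recorded as rejection". The liver paragraph repeats it, beginning "If the ALT returns to baseline without further treatment". The converse is: "If the participant requires more than baseline levels of IS or receives specific treatment for rejection, the event will be recorded as rejection".

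Four other places bear on the same event.

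- **Study Definitions Page, Acute Rejection.** Biopsy-proven cellular rejection, borderline included, and antibody-mediated rejection count by Banff 2019 criteria, with no treatment condition. Clinically diagnosed rejection needs a physician's diagnosis "AND for which the patient is treated with steroids, lytic therapy, or an increase in dose or number of immunosuppressive medications". No reference level for the increase is given.
- **Study Definitions Page, IS Reduction Failure.** The participant resumes baseline IS "but does not receive definitive treatment for rejection e.g. thymoglobulin, steroids, or a sustained increase in dose or number of immunosuppressive medications".
- **Section 3.3.1** (repeated in the Synopsis and Section 13.2). The secondary endpoint is treated rejection, clinical or biopsy-proven, within 60 days of vaccine.
- **Section 11.5.** The rejection pausing rule covers clinically treated or biopsy-proven events, applied separately to vaccine alone, MMF withdrawal and CNI reduction.

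Section 2.1 hypothesises that reduction does not raise the risk of rejection or de novo donor-specific antibody (dnDSA). Section 13.3 leaves participants and clinical staff unmasked.

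**The concern.** Whether an episode counts as rejection can depend on the arm. In the reduction arm the first response to a persistent graft signal is to step IS back up, and if the laboratory value then settles, Section 6.12 keeps the episode out of the rejection count. A control participant is already at baseline. Any IS increase given to a control for diagnosed rejection goes above baseline and counts.

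The episodes set aside are then not used. IS Reduction Failure is defined but appears in none of Sections 3.3, 11.5, 13.2 or 13.4.3. The rejection half of the Section 2.1 hypothesis, and the pausing counts for the two reduction groups, could therefore miss the milder, reversible rejections that a short reduction might cause.

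**Working it through.** **Step 1. One case under each text.** Take a reduction-arm kidney recipient with a persistent creatinine rise in week 1 and a borderline biopsy. Baseline IS is resumed and creatinine returns to baseline.

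| Text | Counted as rejection? |
|---|---|
| Definitions, biopsy-proven | Yes |
| Section 11.5 pausing rule | Yes (biopsy-proven) |
| Section 3.3.1 endpoint | Only if return to baseline IS is treatment; not stated |
| Section 6.12 | No |
| IS Reduction Failure | Fits that category, which nothing uses |

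Without a biopsy, but with a physician's diagnosis of rejection, the clinical definition turns on whether restoring a reduced dose is an increase in dose. The failure definition uses a different term, a sustained increase. Two sites could code the same patient differently, and each would be following the protocol.

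**Step 2. The plan's own figure.** The only stated figure that depends on the rejection count is the pausing table (7 events in 200, 11 in 400). I could not reproduce it. I used a threshold of 3 x (5 to 6)/400 and took the smallest count with posterior probability above 0.5 (Beta(1,1) or Beta(0.5,0.5) prior), or the smallest count whose observed rate exceeds the threshold. These give 15-19 events at n = 400 and 7-10 at n = 200. The prior and method are not stated, so I take the table as given and do not call it wrong.

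**Step 3. Illustration of size.** Inputs from the documents are 5-6 expected rejections in the study (Section 11.5; midpoint 5.5), 200 per arm (Section 13.7) and Fisher's exact test (Section 13.4.3). My assumptions are a true threefold rate in the reduction arm, a two-sided 0.05 level, and a share f of that arm's rejections set aside under Section 6.12.

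- Base rate: 5.5/400 = 1.375%. Control events: 200 x 1.375% = 2.75.
- True reduction-arm events: 3 x 2.75 = 8.25. Recorded: 8.25 x (1 - f).
- Apparent ratio: 3 x (1 - f).

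| f (assumed) | Recorded events | Apparent ratio | P(at least 7 of 200) | Fisher power |
|---|---|---|---|---|
| 0 | 8.25 | 3.0 | 72% | 27% |
| 25% | 6.19 | 2.25 | 42% | 12% |
| 50% | 4.12 | 1.5 | 12% | 3% |
| 67% | 2.75 | 1.0 | 2% | 1% |

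With 5 or 6 expected events instead of 5.5, P(at least 7 of 200) is 63% or 80% at f = 0, and 8% or 17% at f = 50%.

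**Step 4. Limits of the illustration.**

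- The 5-6 events are for the whole study, not the 60-day endpoint.
- Pausing is by MMF and CNI group, not for 200 pooled.
- Section 6.12 acts on rises during reduction, which ends two weeks after vaccine (Section 6.7.1). About 14 of the 60 endpoint days (23%) are directly exposed.
- f is applied to background events too. Losing 50% of 8.25 is 4.125 events, or 4.125/5.5 = 75% of the 5.5 excess. If only excess events can be set aside and half of them are, the recorded count is 2.75 + 2.75 = 5.5, the ratio is 2.0, P(at least 7 of 200) is 31% and Fisher power is 8%.

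**The case against.** The strongest defence is that Section 6.12 deals with a laboratory rise, not with diagnosed rejection. The return to baseline IS is triggered by the laboratory value alone, so calling it rejection therapy could bias the comparison the other way. A control's rise that settles untreated is not recorded as rejection either. Read with the IS Reduction Failure definition, the intended rule may be the same for both arms: count IS above baseline, or specific rejection therapy. That is a fair reading for clinically diagnosed episodes, but the Acute Rejection definition does not say it. It also leaves the conflict over biopsy-proven episodes, for which Section 6.12 makes no exception.

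A reader might infer more: that all alloimmune harm is under-counted, or that Section 6.12 demonstrably hides rejections. The documents support neither. dnDSA, graft loss and death do not depend on Section 6.12, and dnDSA has its own interim comparison (Section 13.5.2), although it is scheduled for kidney recipients only. A transient rise is not proven rejection. Section 6.12 does not say that it overrides the definitions, so biopsy-proven cases may still reach the pausing count.

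The underlying data are also collected. IS medication is recorded through Week 6, adverse events are followed in the reduction arm until 30 days after return to full IS, and the DSMB sees a listing of all AEs. The gap is in classification and prespecified reporting. An unplanned reconstruction from those records would not feed the pausing counts.

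Finally, even with nothing set aside, Fisher power for a true tripling is only 27%. The comparison is weak under any recording rule.

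**Conclusion.** The point holds for rejection. Sections 6.12, 3.3.1 and 11.5 and the two definitions do not give one answer for the same episode. The rule that sets episodes aside operates in one unmasked arm, and the category that receives them is not analysed. Following the plan can therefore under-count rejection in the reduction arm only, in the direction of no increased risk.

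How often this would happen cannot be derived from the documents. The 1.5-fold figure rests on an assumed 50% loss and an assumed true tripling; 2.0-fold results if half of the excess events alone are lost. Both illustrate sensitivity and are not estimates. With so few events expected, moving two or four of them changes the apparent ratio materially, which is reason enough to settle the rule before the safety data are classified.

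**What to change.** 1. Reconcile the Acute Rejection and IS Reduction Failure definitions with Sections 3.3.1, 6.12 and 11.5 so that one recording rule applies to both arms. A biopsy-proven episode counts as rejection in the endpoint and the pausing counts, whatever the response to it. For a physician-diagnosed episode without biopsy, state whether return to baseline IS is treatment or an increase in dose. Carry any change to the endpoint wording into the Synopsis and Section 13.2, and correct the failure definition's reference to Section 6.7, since the criteria are in Section 6.12.
2. Prespecify IS Reduction Failure as a reported safety outcome in Sections 3.3.1 and 13.4.3. Tabulate it alone, and combined with rejection, by arm and reduction group (MMF withdrawal, CNI reduction) as a sensitivity analysis. Give it to the DSMB beside the rejection pausing counts.
3. If creatinine or ALT rises are to be compared between arms, use only scheduled values collected alike in both. The 1-3 day repeat is specified only during reduction. Section 8.3.3 promises weekly hepatic panels for liver recipients, but Appendices 2 and 3 show them only at Day 0 and Month 6, so those passages must be reconciled first.

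Items 1 and 2 cost wording and one additional table. Item 3 could require control-arm testing that the appendices do not show. The downside is that the combined count includes some non-immune rises and is more readily met in the reduction arm, so it is supportive only. No change to patient management is proposed.
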